11. DEMOGRAPHIC AND OTHER BASELINE CHARACTERISTICS

The following demographic data and Baseline characteristics reported in the Study APD334-302 will be summarized by treatment group for the FAS.

- Age on consent (years)
- Sex

- Woman of childbearing potential (Yes/No)
- Height (cm)
- Weight (kg)
- Body Mass Index (BMI) (kg/m²)
- Alcohol consumption (Yes/No)
- Caffeine consumption (Yes/No)
- Tobacco use (Yes/No)

The following Baseline characteristics related to UC reported in the Study APD334-302 will also be summarized by treatment group:

- Extent of disease (Proctosigmoiditis, Left-sided colitis, Pancolitis, Proctitis reported on the electronic case report form [eCRF], and Proctitis reported from Bioclinica Central Read) at APD334-302 study entry
- Baseline MMS
- Baseline rectal bleeding (RB) subscore
- Baseline stool frequency (SF) subscore
- Baseline endoscopic subscore
- Baseline physician's global assessment (PGA)
- Baseline TMS
- Duration of UC (years)
- Any acute exacerbations within past 12 months prior to APD334-302 study entry (Yes/No), including the number of acute exacerbations among those with any acute exacerbation = Yes
- Colonoscopy within past 12 months prior to APD334-302 study entry (Yes/No)
- Surgery for UC (Yes/No) at APD334-302 study entry, including the number of surgeries among those with surgery for UC = Yes
- Hospitalizations for UC (Yes/No), including the number of hospitalizations at APD334-302 study entry
- Naïve to biologic/JAK inhibitor therapy at APD334-302 study entry (Yes/No) – Reported (used for stratification at randomization)
- Naïve to biologic/JAK inhibitor therapy at APD334-302 study entry (Yes/No) – Actual (medications reported on the eCRF)
- Baseline Corticosteroid use (Yes/No) – Reported (used for stratification at randomization)

- Baseline Corticosteroid use (Yes/No) – Actual (medications reported on the eCRF)
- Baseline MMS group (4 to 6, 7 to 9) – Reported (used for stratification at randomization)
- Baseline MMS group (4 to 6, 7 to 9) – Actual (scores reported on the eCRF)
- Naïve to biologic/JAK inhibitor therapy at APD334-302 study entry – Difference between the Reported and the Actual
- Baseline Corticosteroid use (Yes/No) – Difference between the Reported and the Actual
- Baseline MMS group (4 to 6, 7 to 9) – Difference between the Reported and the Actual
- Prior failure of oral 5-ASA only (Yes or No)
- Prior failure of anti-TNF α (Yes or No)
- Prior failure of anti-TNF α or vedolizumab (Yes or No)

Prior treatment for UC will be summarized, including category of treatment, reason for discontinuation, and estimated duration (weeks) of corticosteroid use over the last 12 months.

11.1. Derivations

- Duration of UC (year) = (Informed consent date at APD334-302 – Date of diagnosis + 1) / 365.25
- Weight (kg) = Weight (lb) \times 0.4536
- Height (cm) = Height (in) \times 2.54
- Height (m) = Height (in) \times 0.0254 = Height (cm) \times 0.01
- BMI (kg/ m²) = weight (kg) / height (m)²

12. MEDICAL HISTORY

Medical history not previously collected in Study APD334-302 will be collected on the medical history eCRF and coded using Medical Dictionary for Regulatory Activities (MedDRA, v24.1). The version used to code medical history will be displayed in the outputs. All medical history in APD334-308 will be summarized for the Safety Set by system organ class (SOC) and preferred term (PT).

13. MEDICATIONS AND NON-DRUG TREATMENT

13.1. Medications

Medications will be captured on the Concomitant Medications eCRF and coded using the WHO Drug dictionary (WHODDE01SEP2021). Refer to APPENDIX 2 for handling of partial dates for medications. In the case where it is not possible to define a medication as prior or concomitant, the medication will be classified by the worst case (ie, concomitant).

- ‘Prior’ medications are medications which started and stopped prior to the first dose of study treatment in study APD334-302.
- ‘Concomitant’ medications in study APD334-308 are medications which started prior to, on or after the first dose of study treatment in APD334-308 AND ended on or after the date of first dose of study treatment in APD334-308 or were ongoing at the end of this study.

All medications will be listed. Concomitant medications in ADP334-308 that continue from the Study APD334-302 will be flagged in the listing.

13.2. Non-Drug Treatment

Non-drug treatment will be captured on the Concomitant Non-drug treatment eCRF and coded using MedDRA Version 23.1 or newer.

- ‘Prior’ medications are medications which started and stopped prior to the first dose of study treatment in Study APD334-302.
- ‘Concomitant’ medications in study APD334-308 are medications which started prior to, on or after the first dose of study treatment in APD334-308 AND ended on or after the date of first dose of study treatment in APD334-308 or were ongoing at the end of this study.

Concomitant non-drug treatment in ADP334-308 will be reported in listing and those continue from the Study APD334-302 will be flagged in the listing.

14. STUDY TREATMENT EXPOSURE

The date of first and last study treatment administration in Study APD334-308 will be taken from eCRF. Interruptions, compliance, and dose changes are taken into account for duration of exposure. Exposure to study treatment in weeks will be summarized for the Safety Set.

Dose interruptions will be recorded on the Dosing Administration eCRF, and overdose will be recorded on the Overdose eCRF. The frequency and percentage of subjects who had at least one dose interruption, who had at least 1 dose interruption of > 7 days, who had at least 1 dose interruption of > 14 days, who had 1 overdose, and who had > 1 overdose will be summarized.

14.1. Derivations

Duration of exposure (weeks) in Study APD334-308 = (date of last study treatment administration – date of Week 12 study treatment administration in Study APD334-302 + 1) / 7. For subjects with missing Date of Last Dose on the End of Study eCRF, their date of last study treatment administration will be imputed by the last date of all dosing administration start/stop dates recorded.

15. STUDY TREATMENT COMPLIANCE

The total number of tablets expected, total number of tablets taken, total number of tablets missed, overall compliance with study treatment, frequency and percentage of subjects with overall compliance of < 80% or > 120% will be summarized for the Safety Set of APD334-308.

15.1. Derivations

Compliance to study treatment is based on the Drug Accountability eCRF and will be calculated as the total number of tablets taken (total dispensed – total returned) divided by the number of tablets expected during the treatment period, expressed as a percentage, refer to calculations below.

The total number of tablets expected is defined as the number of tablets that a subject is expected to have taken between their first and last study treatment administration and is numerically identical to the subject's overall study treatment exposure, since the medication is to be taken once daily. On any site visit day, the medication is to be held and taken at the site, after all predose assessments have been completed. For example, if a subject took their last dose of study treatment on Day 200 and returned to the site on Day 207 to return the study treatment bottle, then the total number of tablets expected would be 200, not 206.

- Overall compliance to study treatment will be calculated as follows: The total number of tablets returned subtracted from total number of tablets dispensed, divided by the duration of treatment, multiplied by 100

For all bottles not returned, it will be assumed that all dispensed tablets were taken. For each subject, if a high percentage (> 25%) of bottles were not returned by a subject, additional analyses may be done where bottles not returned are excluded from the overall compliance calculation for the subject. In such analysis, the date of last dose or the date of last bottle return, whichever is earlier, will be used as the “date of last dose” in the calculation above.

Both scheduled and unscheduled study treatment dispensations will be used in the compliance calculation. Overall compliance calculations will be performed for the study of APD334-308 and will be used in determining inclusion/exclusion of subjects in the respective Per Protocol Set.

16. EFFICACY OUTCOMES

Unless otherwise stated, the primary efficacy analyses will be based on subject stratum used at the time of randomization in Study APD334-302 for the FAS. Primary and key secondary efficacy analyses will be repeated for all subjects. The following definitions will be used to assess efficacy outcomes:

- Clinical response: A \geq 2 point and \geq 30% decrease from Baseline in MMS, and a \geq 1-point decrease from Baseline in RB subscore or an absolute RB subscore \leq 1
- Clinical remission: SF subscore = 0 (or = 1 with a \geq 1-point decrease from Baseline), RB subscore = 0, and ES \leq 1 (excluding friability)
- Endoscopic improvement: ES of \leq 1 (excluding friability)
- Endoscopic normalization: ES = 0
- Mucosal healing: ES of \leq 1 (excluding friability) with histologic remission measured by a Geboes Index score $<$ 2.0
- Symptomatic remission: SF subscore = 0 (or = 1 with a \geq 1 point decrease from Baseline) and RB subscore = 0
- Complete symptomatic remission: SF subscore = 0 and RB subscore of 0
- Symptomatic response: Decrease from Baseline \geq 30% in both RB and SF subscores
- Noninvasive clinical response: A \geq 30% decrease from Baseline in composite RB and SF, and a \geq 1 point decrease from Baseline in RB subscore or an absolute RB subscore \leq 1

CCI

- Corticosteroid free clinical remission: Clinical remission at Week 52, while not receiving corticosteroids for 12 or more weeks in the 40 Week Treatment Period
- Sustained clinical remission: Clinical remission at both Week 12 and Week 52
- Loss of response:
 - Achieved clinical response at Week 12 in Study APD334-302
 - A \geq 2-point increase from Week 12 in the combined SF + RB scores and combined SF + RB score of ≥ 4 , on 2 consecutive visits (≥ 7 days apart), and
 - Confirmed by centrally read ES ≥ 2 and,
 - Exclusion of other causes for loss of response unrelated to underlying UC (eg, infection)

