6.7.2.1. Permitted Medications for the Treatment of Ulcerative Colitis

Oral 5-ASA, oral corticosteroids, medicinal probiotics, and antidiarrheals are allowed according to the following guidelines. These products should not be started during the treatment period in subjects who are not already receiving them.

- Oral 5-ASA compounds provided the dose is stable
- Oral corticosteroid therapy (prednisone at a stable dose ≤ 20 mg/day or equivalent steroid) provided the dose is stable

- Probiotics (eg, Saccharomyces boulardii) provided the dose is stable
- Antidiarrheals (eg, loperamide) for control of chronic diarrhea

Subjects on existing oral corticosteroid therapy will be tapered during the treatment period (Section 6.7.2.2).

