10.5. Efficacy Endpoint Definitions

The following definitions will be used to assess efficacy outcomes:

- Baseline: Refer to Section 10.1
- Clinical response: A ≥ 2-point and ≥ 30% decrease from baseline in MMS, and a
 ≥ 1-point decrease from baseline in RB subscore or an absolute RB subscore ≤ 1
- Clinical remission: SF subscore = 0 (or = 1 with a \geq 1-point decrease from baseline), RB subscore = 0, and ES \leq 1 (excluding friability)
- Endoscopic improvement: ES of ≤ 1 (excluding friability)
- Endoscopic normalization: ES = 0
- Mucosal healing: ES of ≤ 1 (excluding friability) with histologic remission measured by a Geboes Index score < 2.0
- Symptomatic remission: SF subscore = 0 (or = 1 with a ≥ 1-point decrease from baseline) and RB subscore = 0
- Complete symptomatic remission: SF subscore = 0 and RB subscore = 0
- Symptomatic response: Decrease from baseline ≥ 30% in composite RB and SF subscores
- Noninvasive clinical response: A ≥ 30% decrease from baseline in composite RB and SF, and a ≥ 1-point decrease from baseline in RB subscore or an absolute RB subscore < 1
- Histologic improvement: Geboes Index score < 3.1
- Histologic remission: Geboes Index score < 2.0
- Clinical remission using Total Mayo Clinic score: Total Mayo Clinic Score of ≤ 2 points with no individual subscore of > 1 point
- Clinical response using Total Mayo Clinic score: A ≥ 3-point and ≥ 30% decrease from baseline in Total Mayo Clinic score, and a ≥ 1-point decrease from baseline in RB subscore or an absolute RB subscore < 1

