10.7.1. Key Secondary Efficacy Endpoints

The key secondary efficacy endpoints are:

[figure not shown]
- The proportion of subjects achieving endoscopic improvement at Week 52
- The proportion of subjects achieving symptomatic remission at Week 52
- The proportion of subjects, who had not been receiving corticosteroids for ≥ 12 weeks, achieving clinical remission at Week 52 among subjects receiving corticosteroids at APD334-302 study entry
- The proportion of subjects with mucosal healing at Week 52
- The proportion of subjects achieving clinical remission at both Week 12 of Study APD334-302 and Week 52 of Study APD334-308

[figure not shown]

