Key Secondary Estimand 3	Efficacy of etrasimod on corticosteroid-free clinical remission at Week 52	Enrolled subjects who receive at least 1 dose of etrasimod	The proportion of subjects with clinical remission at Week 52, while not receiving corticosteroids for 12 or more weeks in the 40-Week Treatment Period	Same as the intercurrent event handling strategy for the primary estimand	Difference between etrasimod and placebo in proportion of responders at Week 52
Key Secondary Estimand 4	Efficacy of etrasimod on mucosal healing at Week 52	Enrolled subjects who receive at least 1 dose of etrasimod	The proportion of subjects with ES of \leq 1 (excluding friability) with histologic remission measured by a Geboes Index score $<$ 2.0 at Week 52	Same as the intercurrent event handling strategy for the primary estimand	Difference between etrasimod and placebo in proportion of responders at Week 52

Estimand	Definition	Attribute			
		Population	Variable/Endpoint	Intercurrent Event Handling Strategy	Population-Level Summary Measure
Key Secondary Estimand 5	Efficacy of etrasimod on sustained clinical remission	Enrolled subjects who receive at least 1 dose of etrasimod	The proportion of subjects with sustained clinical remission (clinical remission at both Weeks 12 and 52)	Same as the intercurrent event handling strategy for the primary estimand	Difference between etrasimod and placebo in proportion of responders

^a Intercurrent events include: 1) initiate a rescue medication for UC, 2) have an increase in dose over Baseline levels in their existing UC medication, or 3) have colectomy or ileostomy before the efficacy assessment.

This SAP will analyze on the data collected in APD334-308 (from Week 16 to Week 52). The scope of analysis will be specified in Table/Listing/Figure shells. To fully address study primary objective “to assess the efficacy of etrasimod on clinical remission in Japanese subjects with moderately to severely active ulcerative colitis (UC) at timepoints up to 52 weeks of treatment (12 weeks in Study APD334-302 plus 40 weeks in Study APD334-308)”, after database lock and treatment unblinding, an integrated analysis of Study APD334-302 and Study APD334-308 will be performed for all Japanese subjects who had enrolled in ADP334-302 and covers the complete data from APD334-302 and to APD334-308.

3. STUDY Design

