8.5. Subgroup Analyses

The following subgroups will be assessed for the primary and key secondary endpoints. Baseline is referring to APD334-302:

- Sex (Female/Male)
- Age (\leq or $>$ Median age, and $<$ or \geq 65). This refers to age collected at Screening in Study APD334-302.
- Baseline oral corticosteroid usage (Yes/No)
- Naïve to biologic/JAK inhibitor therapy at APD334-302 study entry (Yes/No)

- Baseline disease activity (MMS: 4 to 6 or 7 to 9)
- Baseline fecal calprotectin (\leq or $>$ median value)
- Baseline total Mayo score (\leq or $>$ 8)
- Duration of UC (\leq or $>$ Median)
- Extent of disease (Proctosigmoiditis/Left-sided colitis, Pancolitis, Proctitis as reported on the eCRF)
 - Proctitis (Yes or No, based on central read)
 - Prior UC treatment of oral 5-aminosalicylic acid (5-ASA) only (Yes or No)
 - Prior UC treatment failure of oral 5-ASA only (Yes or No)
 - Number of prior biologic or JAK inhibitor therapies (1 or $>$ 1)
 - Prior UC treatment failure of anti-tumor necrosis factor alpha (anti-TNF α) (Yes or No)

Additional subgroups may be assessed, if deemed necessary. The medians will be derived based on the FAS for all subgroups cut at the median.

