16.1.7. Primary Analysis of Key Secondary Efficacy Variables

The primary analysis of these key secondary efficacy endpoints will be performed for the FAS. For all key secondary endpoints, the model described in Section 16.1.3 will be used.

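### The SAP redefines corticosteroid-free remission (key secondary) and symptomatic response without listing either change in SAP Section 3.3

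*SAP*

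**What the plan says.** **Corticosteroid-free remission.** Protocol Section 10.7.1 takes subjects off corticosteroids for at least 12 weeks and counts those "achieving clinical remission at Week 52 among subjects receiving corticosteroids at APD334-302 study entry". The synopsis repeats this. SAP Section 16 gives "Corticosteroid free clinical remission: Clinical remission at Week 52, while not receiving corticosteroids for 12 or more weeks in the 40 Week Treatment Period". Key Secondary Estimand 3 in SAP Table 1 has the same condition, "while not receiving corticosteroids for 12 or more weeks in the 40-Week Treatment Period", and the same population as the other estimands, with no restriction to steroid users. SAP Section 16.1.7 then states: "The primary analysis of these key secondary efficacy endpoints will be performed for the FAS".

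**Symptomatic response.** Protocol Section 10.5 asks for a decrease from baseline of at least "30% in composite RB and SF subscores". SAP Section 16 asks for at least "30% in both RB and SF subscores". The next SAP definition, noninvasive clinical response, still uses the composite. SAP Section 16.2 reports symptomatic response at seven visits, Weeks 16 to 52.

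**Declared changes.** SAP Section 3.3 lists two: UC-PRO/SS was not implemented, and the CMH method was removed. SAP Section 1 says the SAP rests on protocol version Original 0.0, the version reviewed here, so no amendment is cited that would explain either new definition.

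**The concern.** Corticosteroid-free remission is meant to show that patients who needed steroids can reach remission without them. With the whole FAS in the denominator, the treatment difference mixes that question with plain remission in subjects who had no steroid to stop. The key secondary label would then sit on a different estimand.

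A programmer following SAP Section 16 literally would code symptomatic response as two separate 30% conditions, which is not the protocol's endpoint.

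The study reports only estimates, 95% confidence intervals and nominal p-values, so what is being estimated is the substance of the result. The protocol also plans to integrate and bridge these data to the global studies, where an endpoint label has to mean one known thing. Someone relying on SAP Section 3.3 would not learn that either definition had moved.

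**Working it through.** The documents give no computed figure for either endpoint, so there is none to reproduce. The check compares the definitions and counts score patterns.

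**1. What the FAS denominator adds**

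- Protocol Section 6.7.2.1, on permitted UC products including oral corticosteroids: "These products should not be started during the treatment period in subjects who are not already receiving them".
- SAP Section 16.1.2 already makes starting a UC rescue medication, or raising a UC medication above baseline, a nonresponse for all efficacy endpoints.
- A subject not on steroids at entry can therefore score differently on this endpoint and on the primary only through steroid use not classed as UC rescue, for example for a non-UC reason.

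Numbers: about 35 subjects are planned (Protocol synopsis). The share on steroids at entry is not given; 20–40% is assumed, with all 35 entering.

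- Users: 35 × 0.20 = 7 to 35 × 0.40 = 14, both arms together.
- Non-users: 35 × 0.80 = 28 down to 35 × 0.60 = 21.
- If the parent study's 2:1 ratio also held among these subjects (23:12), the users would split about 5:2 at 20%, 7:4 at 30% and 9:5 at 40%. The SAP notes that randomization did not control balance in Japan.

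The reported rate becomes f × (rate in users) + (1 − f) × (rate in non-users), where f is the steroid share. With illustrative rates of 20% in users and 40% in non-users:

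| f | Protocol endpoint | SAP endpoint |
|---|---|---|
| 0.20 | 20% | 0.04 + 0.32 = 36% |
| 0.30 | 20% | 0.06 + 0.28 = 34% |
| 0.40 | 20% | 0.08 + 0.24 = 32% |

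With equal rates in users and non-users the percentage does not move. Neither the direction nor the size of the real effect can be read from the documents.

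**2. Symptomatic response**

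RB and SF each run from 0 to 3 (Protocol Section 9.7.1). *Composite* is read as their sum.

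- SAP rule: a one-point fall is 100%, 50% or 33% from a baseline of 1, 2 or 3. Each meets 30%, so the rule amounts to at least a one-point fall in RB and at least a one-point fall in SF.
- Protocol rule: 30% of a baseline sum of 2, 3, 4, 5 or 6 is 0.6, 0.9, 1.2, 1.5 or 1.8. The rule needs a one-point fall in the sum from 2 or 3, and a two-point fall from 4 to 6.
- One point off each subscore is two points off the sum. With both baselines at least 1, every SAP responder is therefore a protocol responder.

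Counting all integer patterns:

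| Patterns | Total | Protocol rule | SAP rule | Protocol only | SAP only |
|---|---|---|---|---|---|
| Both baselines ≥ 1 | 144 | 66 | 36 | 30 | 0 |
| Same, no subscore worsening | 81 | 60 | 36 | 24 (24/60 = 40%) | 0 |
| Both baselines ≥ 2, no worsening | 49 | 37 | 25 | 12 (12/37 = 32%) | 0 |

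Example: RB 2, SF 3 moving to RB 2, SF 1 is a sum of 5 falling to 3, or 2/5 = 40%. That is a protocol response, but RB has not changed, so it fails the SAP rule.

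If one baseline subscore is 0, its percentage change cannot be computed. There are 96 such patterns, and 20 meet the protocol rule. Under SAP Section 16.2.1 these would plausibly become nonresponses, but the SAP does not say so. Whether a zero baseline can occur depends on the APD334-302 entry criteria, which are not in these documents.

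**The case against.** - **The user-only estimate is still planned.** SAP Section 8.5 applies the subgroup "Baseline oral corticosteroid usage (Yes/No" to every key secondary endpoint, and its *yes* level is close to the protocol's population. This stands as mitigation. It still leaves the protocol's endpoint as one subgroup among many while the FAS figure takes its name.
- **An all-subject version is not foreign to the protocol.** Protocol Section 10.7.2 has, as an other secondary endpoint, Week 52 remission with freedom from corticosteroids since several earlier weeks. One of these is Week 40, 12 weeks before Week 52, and there is no restriction to users. That is fair context. It also shows that the protocol kept the two populations apart and made the user-only one key secondary.
- **Disclosure alone would cure the defect, and 7–14 subjects is a poor base for a main analysis.** The small denominator is real and could justify a declared change. It does not justify an undeclared one.
- **The word *both* may be a drafting slip, and *harder* is conditional.** The counts need composite to mean the sum and both baselines to be at least 1. If a zero-baseline subscore were simply skipped, RB 0, SF 3 moving to RB 1, SF 2 would pass the SAP rule (a 33% fall in SF) and fail the protocol rule (no fall in the sum). That limit stands. A slip is less likely because the next definition keeps the composite, and as written the code would differ.
- **Other documents may use the protocol definitions.** The table shells and the separate plan for the integrated analysis cannot be seen. They would not correct the text of this SAP.

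**Conclusion.** The concern holds. Two endpoint definitions in the SAP differ from the protocol version on which it is based, and SAP Section 3.3 declares neither. The key secondary endpoint loses its steroid-user denominator. Symptomatic response becomes strictly harder when the composite is the sum and both baseline subscores are at least 1: with neither subscore worsening, 24 of 60 protocol-responder patterns are lost. Those patterns are equally weighted possibilities, not patients, and the 7–14 users rest on an assumed 20–40% share.

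This should be fixed, but it does not threaten the main result. The primary endpoint is untouched, p-values are nominal, symptomatic response is an other secondary endpoint, and no size of bias can be stated from the documents.

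A lesser point of clarity, not a separate error: the SAP's 12 or more steroid-free weeks within the 40-week period are not said to run up to Week 52. The protocol is only somewhat clearer.

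**What to change.** 1. In SAP Table 1 (Key Secondary Estimand 3), Section 16 and Section 16.1.7, make subjects receiving corticosteroids at APD334-302 entry the main analysis of corticosteroid-free remission. Keep the FAS version as supplementary.
2. State that the 12 or more steroid-free weeks are those immediately before the Week 52 assessment.
3. In the symptomatic response definition, replace the two-subscore condition with the protocol's composite.
4. List in SAP Section 3.3, with its reason, any difference from the protocol that is kept.

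The cost is SAP wording and derivation code; steroid use and RB and SF scores are already collected. The drawback is a main analysis on few subjects (7–14 in both arms together under the stated assumption, fewer if some do not enter) with a wide confidence interval, which is why the FAS version stays alongside it.
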